3.6.2 Subgroup analysis

Subgroup analyses will be performed for efficacy variables pre-bronchodilator percentage (%) predicted FEV1 and severe exacerbation for ITT population:

- ICS dose group: participants on the medium or high ICS dose at baseline.
- Blood eosinophil (Giga/L) groups at baseline: ≥ 0.3 , < 0.3 Giga/L.
- FeNO (ppb) groups at baseline: < 20 , ≥ 20 ppb; and < 35 , ≥ 35 ppb.
- Baseline age group (6-8, 9-11 years).
- Number of severe asthma exacerbations experienced in previous year before Visit 1: ≤ 1 , $=2$, >2 .
- Number of severe asthma exacerbations that required hospitalization or urgent medical care in previous year before Visit 1: 0, ≥ 1 .

3.7 TIMING OF STATISTICAL ANALYSIS

A database lock for early analysis will be performed when all enrolled participants complete their Week 24 visit with no impact on the conduct of the study. All analyses described in this SAP up to the data cut-off date will be included. Early analysis of the substudy will support the Japan submission and will be included in the CSR.

A core database lock will be conducted when all participants have completed their 52-week treatment period. Analysis will be based on all data collected up to the data cut-off date and will be considered as the final analyses in the CSR.

The database will be updated at the end of the study for all participants to include the post-treatment follow-up information and updates for the events previously ongoing at the time of the core lock. Additional data between this database lock and last participant completing last visit will be summarized in a CSR addendum.

3.8 CHANGES TO PROTOCOL-PLANNED ANALYSES

There are no statistical changes for this Japan substudy in the protocol amendments.

4 SAMPLE SIZE DETERMINATION

The primary objective of this substudy is to evaluate the efficacy of dupilumab in children 6 to <12 years of age with uncontrolled persistent asthma. Assuming the change from baseline in pre-bronchodilator % predicted FEV1 at Week 12 among the study participants follows a normal distribution with mean of 10.74% and standard deviation of 14.12%, a sample size of 16 will lead to a half-width of the 95% confidence interval being 7.5%. A minimum of 3 participants assigned to treatment in each of the 3 dose regimens is targeted.

The sample size calculations were performed using nQuery Advisor.

5 SUPPORTING DOCUMENTATION

5.1 APPENDIX 1 LIST OF ABBREVIATIONS

| | |
|------------|-------------------------------------------------------------------|
| ACQ-IA: | Asthma Control Questionnaire-Interviewer Administered |
| ADA: | anti-drug antibodies |
| AE: | adverse event |
| AESIs: | adverse events of special interest |
| ALP: | alkaline phosphatase |
| ALT: | alanine aminotransferase |
| AST: | aspartate aminotransferase |
| ATC: | anatomic category |
| BMI: | body mass index |
| CPK: | creatine phosphokinase |
| CV: | coefficient of variation |
| ECG: | electrocardiogram |
| eCRF: | electronic case report form |
| FEF: | forced expiratory flow |
| FeNO: | fractional exhaled nitric oxide |
| FEV1: | forced expiratory volume in one second |
| FVC: | forced vital capacity |
| HLGT: | high-level group term |
| HLT: | high level term |
| ICS: | inhaled corticosteroid |
| IEs: | intercurrent events |
| IgE: | immunoglobuline |
| ITT: | intent-to-treat |
| IVRS/IWRS: | Interactive Voice Response System/Interactive Web Response System |
| LLOQ: | lower limit of quantification |
| LLT: | lower-level term |
| MDI: | metered dose inhaler |
| MedDRA: | Medical Dictionary for Regulatory Activities |
| NIMP: | non-investigational medicinal product |
| PCSA: | potentially clinically significant abnormality |
| PK: | pharmacokinetics |
| PT: | preferred term |
| q2w: | once every 2 weeks |
| SAE: | serious adverse event |
| SCS: | systemic corticosteroids |
| SD: | standard deviation, standard deviation |
| SEM: | standard error of the mean |
| SOC: | system organ class |
| TE: | treatment-emergent |
| TEAE: | treatment-emergent adverse event |
| WHO-DD: | World Health Organization-Drug Dictionary |

5.2 APPENDIX 2 PARTICIPANT DISPOSITIONS

For participant study status, the total number of participants in each of the following categories will be presented by dose regimen group and overall:

- Screened participants.
- Screen failure participants and reasons for screen failure.
- Non-enrolled but treated participants.
- Enrolled participants.
- Enrolled but not treated participants.
- Enrolled and treated.
- Participants who discontinued study treatment period as per protocol.
- Participants who discontinued study treatment by main reason for permanent treatment discontinuation.
- Participants who discontinued from the study.
- Participants who discontinued from the study by main reason for permanent study discontinuation.

Reasons for treatment discontinuation and study discontinuation will be supplied in tables giving numbers and percentages.

A participant will be considered as lost to follow-up at the end of study if he/she is not assessed at the last protocol planned visit.

Protocol deviations

Critical and major protocol deviations (automatic or manual) will be summarized in the enrolled population by dose regimen group and overall as well as displayed separately as related versus not related to COVID-19 if applicable.

5.3 APPENDIX 3 DEMOGRAPHICS AND BASELINE CHARACTERISTICS, PRIOR OR CONCOMITANT MEDICATIONS

Demographics, baseline characteristics, medical surgical history

The following demographics and baseline characteristics will be summarized on enrolled population by dose regimen group and the overall group. Continuous data will be summarized using the number, mean, standard deviation (SD), median, minimum, and maximum of available data. Categorical and ordinal data will be summarized using the number and percentage of participants.

Medical and surgical history will be summarized on enrolled population by system organ class (SOC) and preferred term (PT) sorted by internationally agreed order of SOC and by the decreasing frequency of PT within SOC based on the overall group. Comorbidity history and atopic medical history will be summarized separately.

Demographic variables are

- Baseline age in years (quantitative and qualitative variable: 6-8, 9-11 years).
- Gender (Male, Female).
- Baseline height in cm.
- Baseline weight in kg (quantitative and qualitative variable: ≥ 15 to ≤ 30 , >30 kg).
- Baseline BMI in kg/m² (quantitative and qualitative variable: <20 , ≥ 20 kg/m²).

The following baseline disease characteristics will be summarized:

- ICS dose level at baseline (medium, high).
- Age at asthma onset (years).
- Time since first diagnosis of asthma (years).
- Time since last asthma exacerbation (months).
- Number of asthma exacerbations experienced in previous year before Visit 1 (quantitative and qualitative variable: 1, 2, 3, ≥ 4).
- Number of asthma exacerbations required hospitalization or urgent medical care in previous year before Visit 1 (quantitative and qualitative variable: 0, 1, 2, 3, ≥ 4).
- Baseline eosinophil count (Giga/L).
- Baseline eosinophil count category (<0.15 , ≥ 0.15 and <0.3 , ≥ 0.3 Giga/L).
- Baseline FeNO (ppb).
- Baseline FeNO category (<20 , ≥ 20 and < 35 , ≥ 35 ppb).
- Baseline spirometry data, including pre-bronchodilator forced expiratory volume in 1 second (FEV1) (L) and percentage (%) predicted FEV1.
- Baseline serum total IgE (IU/mL).

Medical (or surgical) history includes all the relevant medical (or surgical) history during the lifetime of the participant. This information will be coded using the version of Medical Dictionary for Regulatory Activities (MedDRA) currently in effect at Sanofi at the time of database locks.

The following comorbid diseases will be summarized:

- Atopic dermatitis history (Yes, Ongoing condition).
- Allergic conjunctivitis history (Yes, Ongoing condition).
- Allergic rhinitis history (Yes, Ongoing condition).

- Allergic conjunctivitis and/or rhinitis history (Yes, Ongoing condition).
- Chronic rhinitis history (Yes, Ongoing condition).
- Chronic sinusitis history (Yes, Ongoing condition).
- Eosinophilic esophagitis history (Yes, Ongoing condition).
- Food allergy history (Yes, Ongoing condition).
- Hives history (Yes, Ongoing condition).

A participant will be considered to have an atopic medical condition if the participant has any of the following ongoing conditions: atopic dermatitis, allergic conjunctivitis or allergic rhinitis, eosinophilic esophagitis, food allergy, hives; or has baseline total IgE ≥ 100 IU/mL and at least one positive antigen-specific IgE (≥ 0.35 IU/mL) at baseline.

Prior or concomitant medications

All medications taken within 30 days before screening and until the end of the study, including asthma controller medications, reliever medications and systemic corticosteroids are to be reported in the electronic case report form (eCRF) pages.

All medications will be coded using the World Health Organization-Drug Dictionary (WHO-DD) using the version currently in effect at Sanofi at the time of database locks.

- Prior medications are any treatments taken by participant prior to the first IMP administration in the study.
- Concomitant medications are any treatments received by participant concomitantly to the IMP in the study, from (on/after) the first administration of IMP to the last administration + 98 days. A given medication can be classified both as a prior medication and as a concomitant medication.

The prior and concomitant medications will be summarized for the enrolled population by dose regimen group and overall.

Medications will be summarized according to the WHO-DD dictionary, considering the first digit of the anatomic category (ATC) class and the first 3 digits of the ATC class (therapeutic category). All ATC codes corresponding to a medication will be summarized, and participants will be counted once in each ATC category (anatomic or therapeutic) linked to the medication. Therefore participants may be counted several times for the same medication.

The table for prior medications and concomitant medications will be sorted by decreasing frequency of ATC followed by all other therapeutic classes based on the overall incidence. In case of equal frequency regarding ATCs (anatomic or therapeutic categories), alphabetical order will be used.

The ICS in combination with controller medication(s) and reliever medications will be summarized separately.

ICS in combination with controller medications

Participants may use albuterol/salbutamol or levalbuterol/levosalbutamol metered dose inhaler (MDI) as reliever medication as needed during the study. Nebulizer solutions may be used as an alternative delivery method.

ICS in combination with controller medications within 30 days prior to screening of the study will be summarized on the enrolled population by dose regimen group and overall, and will be sorted by decreasing frequency of standard medication name in the overall category.

The prescription of ICS in combination with controller medication(s) at enrollment will be summarized. Number (%) of participants will be presented by medication names and ICS dose level (medium/high) according to the classification specified in (1).

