17.7.2.5.2 Duration of study participation

17.7.2.5.2.1 Duration of study participation for each patient

The total duration, per patient, is of approximately 68 weeks.

For each patient, this includes the following 3 periods:

- **Screening period:** 4 ±1 weeks.
- **Treatment period:** 52 weeks open-label treatment (1 year) with last dosing at Week 50 for q2w and at Week 48 for q4w.
- **Post-treatment period:** 12 weeks.

17.7.2.5.2.2 Determination of end of clinical trial (all patients)

See [Section 6.2.2](#).

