2.1.2 Prior or concomitant medications

All medications taken within 30 days before screening of parent study and until the end of LTS14424 study, including asthma controller medications, reliever medications and systemic corticosteroids are to be reported in the electronic case report form (eCRF) pages.

All medications will be coded using the World Health Organization-Drug Dictionary (WHO-DD) using the version currently in effect at Sanofi at the time of database locks.

- Prior medications are any treatments taken by patient prior to the first IMP administration in the parent study. Prior medications can be discontinued before the first IMP administration in parent study or can be maintained during treatment phase in parent study.
- Concomitant medications in parent study are any treatments received by patient concomitantly to the IMP in the parent study, from (on/after) the first administration of IMP up to the last available information in parent study before rolling over into the LTS14424 study.
- Concomitant medications are any treatments received by patient concomitantly to the IMP in the LTS14424 study, from (on/after) the first administration of IMP to the end of post-treatment follow-up period. A given medication can be classified both as a prior medication and as a concomitant medication.

2.1.2.1 *Salbutamol/albuterol or levosalbutamol/levalbuterol reliever medication*

Patients may use albuterol/salbutamol or levalbuterol/levosalbutamol metered dose inhaler (MDI) as reliever medication as needed during the study. Nebulizer solutions may be used as an alternative delivery method.

The reliever medication will be recorded as number of puffs in eCRF. The conversion factor is shown as below.

| Salbutamol/Albuterol nebulizer solution-total daily dose (mg) | Number of Puffs* |
|---------------------------------------------------------------|------------------|
| 2.5 | 4 |
| 5.0 | 8 |
| 7.5 | 12 |
| 10 | 16 |

*Conversion factor: salbutamol/albuterol nebulizer solution (2.5 mg) corresponds to 4 puffs

- Example of salbutamol/albuterol nebulizer-to-puff conversion: patient received 3 salbutamol/albuterol nebulizer treatments (2.5 mg/treatment) between 7 and 11 AM.
Total = 7.5 mg → 12 puffs.

| Levosalbutamol/Levalbuterol nebulizer solution-total daily dose (mg) | Number of Puffs* |
|----------------------------------------------------------------------|------------------|
| 0.63 | 2 |
| 1.25 | 4 |
| 2.5 | 8 |
| 3.75 | 12 |
| 5 | 16 |

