3 STATISTICAL ANALYSES

3.1 GENERAL CONSIDERATIONS

In general, continuous data will be summarized using the number, mean, standard deviation (SD), median, minimum, and maximum for observed data and the change from baseline. Categorical and ordinal data will be summarized using the count and percentage of participants.

The baseline values for efficacy, safety, PK, ADA and other endpoints are defined as the last available measurements prior to the first IMP dose if the participant is treated, or the last available value up to enrollment if the participant is not exposed to IMP.

Unless otherwise specified, all analyses will be performed on each dose regimen group and overall.

Observation period

The observation period will be divided into 4 segments:

- The **pre-treatment period** is defined as the period up to first IMP administration.
- The **treatment-emergent (TE) period** is defined as the period from the first IMP administration to the last IMP administration + 98 days for participants with IMP on 100 mg/200 mg q2w regimen, or to the last IMP administration + 112 days for participants on 300 mg q4w regimen. The treatment-emergent period includes the following 2 periods:
 - The **on-treatment period** is defined as the period from the first IMP administration to the last administration of the IMP + 14 days for participants with IMP on 100 mg/200 mg q2w regimen, or to the last administration of IMP + 28 days for participants on 300 mg q4w regimen.
 - The **residual treatment period** is defined as the period from the end of the on-treatment period to the end of the treatment-emergent period.
- The **post-treatment period** is defined as the period from the end of the treatment-emergent period.

The on-study observation period is defined as the time from start of intervention until the end of the study defined as the status date collected on e-CRF page “Completion of End of Study”.

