For the efficacy assessment, the reference date for the derivation of relative days of events or findings will be the day of the first IMP injection. And for the endpoints not measured daily, all available values of scheduled measurements will be assigned to the appropriate visit window according to [Table 7](#). In the event of multiple measurements of the same test in the same window, the one closest to the targeted visit date will be used for the by-visit summary. If they are at the same distance to the target day, the latest one will be used.

Table 7 - Time window for efficacy variables

| Visit | Target day | Time windows for | |
|------------------------|------------|---------------------|---------------------|
| | | Spirometry | ACQ-IA |
| Visit 0 (Week -4±1) | -28±7 | < -14 | < -14 |
| Visit 1 (Week 0) | 1 | -14 - 1- | -14 - 1- |
| Visit 2 (Week 2) | 15 | 1 ⁺ - 21 | 1 ⁺ - 21 |
| Visit 3 (Week 4) | 29 | 22 - 42 | 22 - 42 |
| Visit 4 (Week 8) | 57 | 43 - 70 | 43 - 70 |

| Visit | Target day | Time windows for | |
|----------------------------|------------|------------------|-----------|
| | | Spirometry | ACQ-IA |
| Visit 5 (Week 12) | 85 | 71 - 126 | 71 - 126 |
| Visit 6 (Week 6) | 113 | | |
| Visit 7 (Week 20) | 141 | | |
| Visit 8 (Week 24) | 169 | 127 - 266 | 127 - 210 |
| Visit 9 (Week 36) | 253 | | 210 - 308 |
| Visit 10 (Week 52, EOT) | 365 | 267 - 406 | 309 - 406 |
| Visit 11 (Week 64, EOS) | 449 | > 406 | > 406 |

Note: 1: Up to 1st IMP dose date/time; 1+: after 1st IMP dose date/time.

For the pharmacokinetics/pharmacodynamics variables summary, the reference date for the derivation of relative days of measurements will be the date of first IMP dose injection. Pharmacodynamics variables will be summarized by the analysis window as defined in [Table 8](#) by visit descriptive analyses. All available values of scheduled measurements will be assigned to the appropriate visit window. In the event of multiple measurements of the same test in the same window, the one closest to the targeted visit date will be used for the by-visit summary. If they are at the same distance to the target day, the latest one will be used.

Table 8 - Time window for pharmacokinetics and pharmacodynamics variables

| Visit | Target day | PK, ADA | Time windows for | |
|------------------------|------------|---------|-------------------------------------|----------|
| | | | Serum total IgE and Ag-specific IgE | FeNO |
| Visit 0 (Week -4±1) | -28±7 | | | < -14 |

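### The Japan substudy SAP closes the concomitant-medication window at last dose + 98 days for all regimens, 14 days too early for children completing 300 mg q4w

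*SAP*

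**What the plan says.** Japan substudy SAP, Section 5.3 (Appendix 3), defines concomitant medication as treatment received "from (on/after) the first administration of IMP to the last administration + 98 days". No alternative is given for q4w. The same section has all medications reported in the eCRF until the end of the study, and tabulates prior and concomitant medications by dose regimen and overall.

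Section 3.1 of that SAP does split by regimen. For the two q2w regimens, treatment-emergent time runs "to the last IMP administration + 98 days for participants with IMP on 100 mg/200 mg q2w regimen". The q4w regimen is given its own, longer limit, namely "to the last IMP administration + 112 days for participants on 300 mg q4w regimen". Protocol Section 17.7.2.10.4.3 agrees, with 14 weeks after the last injection for q2w and 16 weeks for q4w.

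Protocol Section 17.7.2.5.2 sets a 52-week treatment period "with last dosing at Week 50 for q2w and at Week 48 for q4w". The Japan SAP's visit-window tables (Section 5.4) put the end-of-study visit at "Visit 11 (Week 64, EOS) | 449".

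The main-study SAP, Section 2.1.2, uses no fixed number of days. Its window runs "from (on/after) the first administration of IMP to the end of post-treatment follow-up period".

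**The concern.** The 98-day figure is the q2w treatment-emergent length applied to all three regimens. Elsewhere the Japan SAP separates q2w from q4w: in the treatment-emergent and on-treatment periods (Section 3.1) and in exposure duration (Section 3.5.1, + 15 against + 29 days). No reason is given for a single figure here, so it looks like an oversight.

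The columns of a by-regimen table would then rest on different lengths of follow-up. For a q4w child who completes treatment, a drug first started on Day 440, say, falls after the concomitant window and cannot be prior. The Japan SAP has no third category for it. The same drug on the same day in a q2w child who completes treatment is tabulated.

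**Working it through.** Day numbering takes the first dose as Day 1, so Week w is Day 7w + 1.

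**Inputs**
- Last scheduled dose (Protocol 17.7.2.5.2): q2w Week 50 = Day 351; q4w Week 48 = Day 337.
- End-of-study visit (Japan SAP 5.4): Week 64 = Day 449.
- Concomitant window (Japan SAP 5.3): last dose + 98 days, all regimens.
- Treatment-emergent period (Japan SAP 3.1): last dose + 98 days for q2w, + 112 days for q4w.

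**The plan's own lengths.** Dose interval plus 12 weeks: q2w 14 + 84 = 98 days; q4w 28 + 84 = 112 days. Both match Section 3.1, and 98 is therefore the q2w length.

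**Window ends for children dosed to schedule**

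| | q2w | q4w |
|---|---|---|
| Concomitant window ends | 351 + 98 = Day 449 (Week 64) | 337 + 98 = Day 435 (Week 62) |
| Treatment-emergent period ends | 351 + 98 = Day 449 | 337 + 112 = Day 449 |
| Shortfall to Week 64 | 0 days | 14 days |
| Shortfall to treatment-emergent end | 0 days | 14 days |

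**Size.** The window is defined from the first dose onward, so the loss is 14/449 = 3.1% of it.

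**Permitted timing.** Allow d = ±3 days on the last dose and v = ±7 days on the Week 64 visit.
- q4w shortfall to the visit = (448 + v) − (336 + d) − 98 = 14 + v − d, which is 4 to 24 days.
- q2w shortfall = (448 + v) − (350 + d) − 98 = v − d, which is −10 to 10 days, centred on zero.

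**Early discontinuation.** Under Protocol 17.7.2.9 the early EOT visit is 2 weeks after the last injection where possible, and the early EOS visit is 12 weeks later: 14 + 84 = 98 days after the last dose. A q4w child on that schedule nominally has no gap.

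**Number of children.** Japan SAP 1.1 reports 13 enrolled with at least 3 on each of three regimens. The q4w group is therefore 3 to 13 − 3 − 3 = 7 children.

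**After correction.** With + 112 days for q4w, 337 + 112 = Day 449 and the shortfall is 0, as for q2w.

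**The case against.** The strongest reply is that the mismatch has almost no consequence, and most of that reply stands.

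- **Week 64 results.** A reader might infer that the gap distorts Week 64 spirometry, ACQ-IA, FeNO or IgE, because it falls just before those assessments. The documents do not support this. The only intercurrent event defined is discontinuation of study intervention, handled by treatment policy without imputation (Japan SAP 1.2.1, 3.2, 3.3), and the biomarkers are plain descriptive summaries (3.6.1.3). None of these analyses uses the concomitant-medication classification.
- **Controller step-ups.** A child is counted once per ATC category (5.3). Children enter on inhaled corticosteroid, so a dose increase in that fortnight adds nothing to any column. A cell changes only if the first use of a category since the first dose falls there.
- **Biologics.** These are a weak example: Protocol 8.8.1, to which the Japan section refers through 8.8, bars them during the study.
- **Adverse events.** An event in the fortnight is treatment-emergent for q4w while a drug newly started for it is not concomitant. This is an inconsistency of definition only. Corrective treatment is recorded with the event itself (Protocol 10.4.3), and no adverse-event table draws on the medication classification.
- **Exacerbation rate.** It is counted only to Week 52 or last contact (3.3), so it is unaffected.
- **A larger percentage.** Setting 14 days against the 84 post-treatment days gives 17%, but the SAP plans no medication table confined to those 84 days.

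The inconsistency itself survives. No other section supplies a q4w end point for this window, and collecting the data to end of study does not place them in the table.

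**Conclusion.** The point holds as a small internal inconsistency. For q4w children who take their last dose at Week 48 as scheduled, the concomitant window ends 14 days before Week 64 and before their own treatment-emergent period ends; for q2w children the shortfall is zero. The q4w column of the descriptive medication table can therefore be understated relative to the q2w columns. Whether it is depends on a child first using a new medication class in that fortnight, which the documents cannot tell us.

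The affected group is 3 to 7 of 13 children, less any who stop early and follow the early EOT/EOS schedule. Medications started by Day 435 and continuing are still counted. Data arriving after the core lock go to a CSR addendum (Japan SAP 3.7), so some of the affected entries would appear only there. The primary endpoint and all other efficacy, safety and biomarker results are untouched.

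**What to change.** In Japan SAP Section 5.3, replace the single 98-day end with the end of the treatment-emergent period already defined in Section 3.1: last administration + 98 days for the q2w regimens and + 112 days for 300 mg q4w. Alternatively, end the window at the close of post-treatment follow-up, as Section 2.1.2 of the main-study SAP does. Either brings scheduled q2w and q4w completers to Day 449.

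The cost is one phrase and one derivation line. No new data are needed, because medications are already collected to the end of the study, and no other table has to be rerun.
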